**b. Relationship to Study Device or Surgical Procedure**

- **Related:** There is at least a reasonable possibility the AE is related to the study device or surgical procedure. Reasonable possibility means there is evidence to suggest either a causal relationship or association between the study device or surgical procedure and the AE.
- **Unrelated:** There is little or no reasonable possibility the AE is related to the study device or surgical procedure. No reasonable possibility means there is no evidence to suggest either a causal relationship or association between the study device or surgical procedure and the AE.

**12.4.4 Reporting**

Actions required by Investigators for reporting non-serious ocular adverse events are summarized in **Table 1** below.

**Table 1. Non-serious Adverse Events**

Non-serious ocular AEs	Non-device-related	Device-related
Required Action	Recorded on Adverse Event CRF only; no expedited report to Sponsor; no report to IRB	

Actions required by Investigators for reporting all serious adverse events are summarized in **Table 2** below.

**Table 2. Serious Adverse Events**

SAEs (ocular and non-ocular)	Non-device-related	Device-related	
		Anticipated	Unanticipated
Required Action	Recorded on SAE/UADE Report Form and AE CRF ↓ Investigator submits expedited report to Sponsor and its representative within 48 hours; report to IRB, if required per IRB policy	Recorded on SAE/UADE Report Form and AE CRF ↓ Investigator submits expedited report to Sponsor and its representative within 48 hours; Investigator reports to IRB within 10 working days or per IRB policy, whichever is shorter	Sponsor Conducts Evaluation ↓ Sponsor or its representative reports to FDA, all IRBs & all Investigators within 10 working days

#### **12.4.4.1 On-Site SAE and UADE Reporting**

The Investigator must report any adverse event to the Sponsor and its representative in an expedited manner if it meets the criteria for a SAE or UADE. The Investigator must forward the SAE/UADE Report Form and any available supporting documents to the Sponsor or its designee within 48 hours of becoming aware of an event.

The contacts for reporting SAEs/UADEs are:

The Investigator must also report UADEs to the reviewing IRB/IEC within 10 working days following awareness of the UADE or according to the established reporting procedures of the IRB, whichever is shorter. The Investigator should also complete applicable CRFs within 3 working days of event identification. The Sponsor or its representative will report the UADE

to the FDA, all other IRBs, and all Investigators within 10 working days after first being informed by the Investigator.

#### **12.4.4.2 Off-Site UADE Reporting**

[figure not shown]
When participating in multicenter clinical investigations, Principal Investigators may receive off-site UADE reports. These are Sponsor reports of UADEs which occurred at other clinical sites for the same trial, or in different trials using the same test article, that met the criteria for reporting to a regulatory agency. These should be reported to the reviewing IRB/IEC within 10 working days or per their established reporting procedures, whichever is shorter.

#### **12.4.4.3 Reporting Device Deficiencies**

A device deficiency is defined as an inadequacy of a medical device with respect to its identity, quality, durability, reliability, safety or performance. Device deficiencies include malfunctions, use errors, and inadequate labeling.

Investigators must evaluate, record, and report via applicable forms any complaints/deficiencies or malfunctions experienced with a Test or Control lens during this trial to the Sponsor and its representative promptly. The Sponsor shall review all device deficiencies, and, upon the Sponsor's request, Investigators must supply any additional information related to the safety reporting of a particular event.

The contact for reporting device deficiencies is:

#### **12.4.5 Adverse Events at Subject Exit**

Ongoing AEs will be followed until resolution, no further change in the condition is expected (i.e., event stabilized), or as dictated by standard of care. Documentation in the CRF of this follow-up is not required although subject care should continue as appropriate.

Ongoing UADEs will be followed by the Sponsor and its representative(s) and the Investigator until the outcome is determined or until no further change in the condition is expected.

[figure not shown]
#### **12.4.6 Pregnancy**

During the study, all female subjects of childbearing potential should be instructed to contact the investigator immediately if they suspect they might be pregnant (e.g., missed or late menstrual period). Female subjects who become pregnant during the study will be followed until completion of pregnancy. Every effort will be made to obtain the health status of the mother and infant or fetus (in cases of miscarriage or therapeutic abortion) at term. Pregnancy itself is not considered an AE.

All confirmed pregnancies must be immediately reported to the medical monitor and CRO contact within 48 hours of the investigator's awareness of the pregnancy. All confirmed pregnancies must be reported via confirmed facsimile or email transmission and must be

submitted on a Pregnancy Report form to the Sponsor or designee within 48 hours of the investigator's awareness of the pregnancy.

The contacts for reporting pregnancies are:

## 13 Statistics

Additional details regarding statistical analyses will be provided in the statistical analysis plan (SAP), which will be prepared and approved prior to database lock.

### 13.1 Study Endpoints

#### 13.1.1 Safety Endpoints

##### 13.1.1.1 Primary Safety Endpoints

- The incidence of all serious adverse events, including SSIs related to the optical properties of the IOL, in first eyes through study exit
- The rate of secondary surgical interventions due to the optical properties of the lens for first eyes through study exit
- The incidence of adverse events in first eyes compared to ISO Safety and Performance Endpoint (SPE) rates as defined in ISO 11979-7 through study exit

##### 13.1.1.2 Secondary Safety Endpoints

- The rates of visual disturbances reported as “severe” by subjects, as well as the rates of visual disturbances reported as “very” bothersome by subjects, using the QoV questionnaire measure through Post-Operative Visit 4 (Day 120 to 180 after second eye IOL implantation)
- Mean photopic contrast sensitivity with glare and mesopic contrast sensitivity with and without glare at Post-Operative Visit 4 (Day 120 to 180 after second eye IOL implantation) and Post-Operative Visit 5 (Day 330 to 420 after second eye IOL implantation)
- Incidence of the types of AEs specified in the co-primary endpoints, but for fellow and “all” eyes
- Incidence of all other types of adverse events in primary eyes, fellow eyes, and “all” eyes

### 13.1.2 Effectiveness Endpoints

#### 13.1.2.1 Primary Effectiveness Endpoints

- Photopic monocular best-corrected distance visual acuity (BCDVA) in first eyes at Post-Operative Visit 4 (Day 120 to 180 after second eye IOL implantation)
- Photopic monocular distance-corrected near visual acuity (DCNVA) in first eyes at 40 cm at Post-Operative Visit 4 (Day 120 to 180 after second eye IOL implantation)
- Photopic monocular distance-corrected intermediate visual acuity (DCIVA) in first eyes at 66 cm at Post-Operative Visit 4 (Day 120 to 180 after second eye IOL implantation)

#### 13.1.2.2 Secondary Effectiveness Endpoints

- Photopic binocular distance-corrected near visual acuity (DCNVA) at 40 cm at Post-Operative Visit 4 (Day 120 to 180 after second eye IOL implantation)
- Photopic binocular uncorrected near visual acuity (UCNVA) at 40 cm at Post-Operative Visit 4 (Day 120 to 180 after second eye IOL implantation)
- Photopic binocular distance-corrected intermediate visual acuity (DCIVA) at 66 cm at Post-Operative Visit 4 (Day 120 to 180 after second eye IOL implantation)
- Photopic binocular uncorrected intermediate visual acuity (UCIVA) at 66 cm at Post-Operative Visit 4 (Day 120 to 180 after second eye IOL implantation)
- First eye BCDVA, DCNVA, and DCIVA evaluated at Visit 5

## 13.2 Hypotheses

The critical region for rejection of null hypotheses will be a p-value  $\leq 0.05$  unless otherwise specified.

### 13.2.1 Safety Endpoints

#### First Primary Safety Endpoint

There is no statistical hypothesis associated with the proportion of first mITT eyes with at least one serious adverse event.

#### Second Primary Safety Endpoint

The second primary safety endpoint is the rate of secondary surgical interventions due to the optical properties of the lens. The null and alternative hypotheses are as follows.

$$\begin{aligned} H_0: \pi_T - \pi_C &\geq 0.034 \\ H_1: \pi_T - \pi_C &< 0.034 \end{aligned}$$

Where:

- $\pi_T$  = the proportion of the Test (trifocal) group first eyes that underwent at least one secondary surgical intervention related to the optical properties of the IOL, and
- $\pi_C$  = the proportion of the Control (monofocal) group first eyes that underwent at least one secondary surgical intervention related to the optical properties of the IOL

- 0.034 is the non-inferiority margin

### Third Primary Safety Endpoint

For each ISO 11979-7 SPE grid AE, the null and alternative hypotheses are as follows:

$$\begin{aligned}H_0: \pi &\leq \pi_0 \\H_1: \pi &> \pi_0\end{aligned}$$

Where:

- $\pi$  = the proportion of Test (trifocal) eyes with the adverse event, and
- $\pi_0$  = the historical control proportion of eyes with the adverse event given in the ISO 11979-7 SPE grid

If none of the null hypotheses are rejected, then it will be concluded that the Test IOL is statistically successful in these outcomes.

### First Secondary Safety Endpoint

There is no hypothesis associated with the incidence of subjects reporting rates of visual disturbances reported as “severe” by subjects, as well as the rates of visual disturbances reported as “very” bothersome by subjects, using the QoV questionnaire measure through Post-Operative Visit 4 (Day 120 to 180 after second eye IOL implantation).

### Second Secondary Safety Endpoint

There is no hypothesis associated with mean photopic or mesopic contrast sensitivity at Post-Operative Visit 4 (Day 120 to 180 after second eye IOL implantation) and Post-Operative Visit 5 (Day 330 to 420 after second eye IOL implantation).

### Third and Fourth Secondary Safety Endpoints

There are no hypotheses associated with these endpoints.

## **13.2.2 Effectiveness Endpoints**

The statistical success of the trial will depend on the statistical success of all three primary effectiveness endpoints.

### First Primary Effectiveness Endpoint

For the first primary effectiveness endpoint, photopic monocular logMAR BCDVA in first eyes at Post-Operative Visit 4, there are three hypotheses to be tested. The Test IOL must be successful in all three hypothesis tests to achieve success in this endpoint.

The first null ( $H_0$ ) and alternative ( $H_1$ ) hypotheses are as follows:

$$H_0: \mu_T - \mu_C \geq 0.10$$

$$H_1: \mu_T - \mu_C < 0.10$$

Where:

- $\mu_T$  = the mean logMAR BCDVA of the Test (trifocal) group, and
- $\mu_C$  = the mean logMAR BCDVA of the Control (monofocal) group

If the null hypothesis is rejected, then it will be concluded that the Test IOL is statistically successful in this evaluation.

The second null ( $H_0$ ) and alternative ( $H_1$ ) hypotheses are as follows:

$$H_0: \pi_T \geq 0.925$$

$$H_1: \pi_T < 0.925$$

Where  $\pi_T$  = the proportion of mITT Set Test (trifocal) group eyes with BCDVA 20/40 or better. The ISO standard specifies a nontraditional evaluation of these hypotheses, with failure to reject the null hypothesis indicating success. If the null hypothesis is not rejected, then it will be concluded that the Test IOL is statistically successful in this evaluation.

The third null ( $H_0$ ) and alternative ( $H_1$ ) hypotheses are as follows:

$$H_0: \pi_T \geq 0.967$$

$$H_1: \pi_T < 0.967$$

Where  $\pi_T$  = the proportion of Best Case Set Test (trifocal) group eyes with BCDVA 20/40 or better. The ISO standard specifies a nontraditional evaluation of these hypotheses, with failure to reject the null hypothesis indicating success. If the null hypothesis is not rejected, then it will be concluded that the Test IOL is statistically successful in this evaluation.

### Second Primary Effectiveness Endpoint

For the second primary effectiveness endpoint, photopic monocular logMAR DCNVA in first eyes at Post-Operative Visit 4, the null and alternative hypotheses are as follows:

$$H_0: \mu_T = \mu_C$$

$$H_1: \mu_T \neq \mu_C$$

Where:

- $\mu_T$  = the mean logMAR DCNVA of the Test (trifocal) group, and
- $\mu_C$  = the mean logMAR DCNVA of the Control (monofocal) group

If the null hypothesis is rejected and the mean for the Test group is less than the mean for the Control group, then it will be concluded that the Test IOL is statistically successful in this outcome.

#### Third Primary Effectiveness Endpoint

For the third primary effectiveness endpoint, photopic monocular logMAR DCIVA in first eyes at Post-Operative Visit 4, the null and alternative hypotheses are as follows:

$$\begin{aligned} H_0: \mu_T &= \mu_C \\ H_1: \mu_T &\neq \mu_C \end{aligned}$$

Where:

- $\mu_T$  = the mean logMAR DCIVA of the Test (trifocal) group, and
- $\mu_C$  = the mean logMAR DCIVA of the Control (monofocal) group

If the null hypothesis is rejected and the mean for the Test group is less than the mean for the Control group, then it will be concluded that the Test IOL is statistically successful in this outcome.

#### First Secondary Effectiveness Endpoint

For the first secondary effectiveness endpoint, photopic binocular DCNVA at Visit 4, the null and alternative hypotheses are as follows:

$$\begin{aligned} H_0: \mu_T &= \mu_C \\ H_1: \mu_T &\neq \mu_C \end{aligned}$$

Where:

- $\mu_T$  = the mean logMAR DCNVA of the Test (trifocal) group, and
- $\mu_C$  = the mean logMAR DCNVA of the control (monofocal) group

If the Test IOL is statistically successful in all primary endpoints with success criteria, the null hypothesis is rejected, and the mean for the Test group is less than the mean for the Control group, then it will be concluded that the Test IOL is statistically successful in this outcome.

#### Second Secondary Effectiveness Endpoint

For the second secondary effectiveness endpoint, photopic binocular UCNVA at Visit 4, the null and alternative hypotheses are as follows:

$$\begin{aligned} H_0: \mu_T &= \mu_C \\ H_1: \mu_T &\neq \mu_C \end{aligned}$$

Where:

- $\mu_T$  = the mean logMAR UCNVA of the Test (trifocal) group, and
- $\mu_C$  = the mean logMAR UCNVA of the control (monofocal) group

If the Test IOL is statistically successful in the first secondary effectiveness endpoint, the null hypothesis is rejected, and the mean for the Test group is less than the mean for the Control group, then it will be concluded that the Test IOL is statistically successful in this outcome.

#### Third Secondary Effectiveness Endpoint

For the third secondary effectiveness endpoint, photopic binocular DCIVA at Visit 4, the null and alternative hypotheses are as follows:

$$\begin{aligned}H_0: \mu_T &= \mu_C \\H_1: \mu_T &\neq \mu_C\end{aligned}$$

Where:

- $\mu_T$  = the mean logMAR DCIVA of the Test (trifocal) group, and
- $\mu_C$  = the mean logMAR DCIVA of the Control (monofocal) group

If the Test IOL is statistically successful in the second secondary effectiveness endpoint, the null hypothesis is rejected, and the mean for the Test group is less than the mean for the Control group, then it will be concluded that the Test IOL is statistically successful in this outcome.

#### Fourth Secondary Effectiveness Endpoint

For the fourth secondary effectiveness endpoint, photopic binocular UCIVA at Visit 4, the null and alternative hypotheses are as follows:

$$\begin{aligned}H_0: \mu_T &= \mu_C \\H_1: \mu_T &\neq \mu_C\end{aligned}$$

Where:

- $\mu_T$  = the mean logMAR UCIVA of the Test (trifocal) group, and
- $\mu_C$  = the mean logMAR UCIVA of the Control (monofocal) group

If the Test IOL is statistically successful in the third secondary effectiveness endpoint, the null hypothesis is rejected, and the mean for the Test group less than the mean for the Control group, then it will be concluded that the trifocal MIOL is statistically successful in this outcome.

#### Remaining Secondary Effectiveness Endpoints

There are no hypothesis tests associated with the remaining secondary effectiveness endpoints of first eye BCDVA, DCNVA, and DCIVA evaluated at Visit 5.

### **13.3 Sample Size Determination**

#### **13.3.1 Phase I / Pilot**

A sample size of 24 DCNVA measurements at each of three distances will yield a probability of at least 98% of selecting the best distance when the difference (in logMAR units) between the best distance and the second-best distance is at least 0.1 and the data are normally distributed with a standard deviation of 0.15. The first 27 Test group subjects will be enrolled in Phase I/Pilot to allow for at least 24 Test group subjects at Visit 3A.

A sample size of 24 DCIVA measurements at each of three distances will yield a probability of at least 98% of selecting the best distance when the difference (in logMAR units) between the best distance and the second-best distance is at least 0.1 and the data are normally distributed with a standard deviation of 0.15. The first 27 Test group subjects will be enrolled in Phase I/Pilot to allow for at least 24 Test group subjects at Visit 3A.

#### **13.3.2 Primary Safety Endpoints**

Regarding the rate of all serious adverse events, for a sample size of 300 subjects, the probability of observing at least one event will be at least 95% when the probability of an event is 1% or greater.

Regarding the rate of secondary surgical interventions due to the optical properties of the lens, the expected Control group rate is 0.1% and the expected Test group rate is 0.5%. With 150 eyes in the Control group and 300 eyes in the Test group, the upper limit of the observed one-sided 95% confidence interval will be expected to be less than 0.034 with 99% power when the Control proportion,  $\pi_C$ , is 0.001 and the Test expected proportion,  $\pi_T$ , is 0.005; results are based on 10000 simulations using the Newcombe-Wilson score method to construct the confidence interval.

ISO 11979-7 Annex B shows the relevant sample size calculations and assumptions for the ISO grid safety endpoints.

#### **13.3.3 Secondary Safety Endpoints**

Regarding the rates of visual disturbances reported as “severe” by subjects, as well as the rates of visual disturbances reported as “very” bothersome by subjects, using the QoV questionnaire measure through Post-Operative Visit 4 (Day 120 to 180 after second eye IOL implantation), no statistical hypotheses will be tested. Therefore, no sample size calculation is required.

Regarding mean photopic (with glare) and mesopic (with and without glare) contrast sensitivity at Post-Operative Visit 4 (Day 120 to 180 after second eye IOL implantation) and Post-Operative Visit 5 (Day 330 to 420 after second eye IOL implantation), no statistical hypotheses will be tested. Therefore, no sample size calculation is required.

Regarding the incidence of the types of AEs specified in the co-primary safety endpoints, but for fellow and “all” eyes, no statistical hypotheses will be tested. Therefore, no sample size calculation is required.

Regarding the incidence of all other types of adverse events in primary eyes, fellow eyes, and “all” eyes, no statistical hypotheses will be tested. Therefore, no sample size calculation is required.

#### **13.3.4 Primary Effectiveness Endpoints**

Approximately the first 24 evaluable Test group subjects and 12 evaluable Control group subjects will be excluded from the near and intermediate visual acuity hypothesis tests, leaving an expected evaluable sample size of approximately 276 Test group subjects and 138 Control group subjects to be included in the near and intermediate visual acuity hypothesis tests.

Regarding the non-inferiority test of BCDVA, when the sample sizes in the groups are 300 (Group 1) and 150 (Group 2), a two group 0.050 one-sided t-test will have 99% power to reject the null hypothesis that the Test and Control IOLs are not equivalent (the difference in means,  $\mu_T - \mu_S$ , is 0.10 or farther from zero in the same direction) in favor of the alternative hypothesis that the means of the two groups are equivalent, assuming that the expected difference in means is 0.00 and the common standard deviation is 0.15.

Regarding the comparisons of BCDVA to the ISO grid, ISO 11979-7 specifies a sample size of approximately 300 completed subjects for this type of investigation.

Regarding the superiority tests of DCNVA at 40 cm and DCIVA and 66 cm, a two-group t-test with a 0.05 two-sided significance level will have 99% power to detect a difference in means of -0.10, assuming that the common standard deviation is 0.15, when the sample sizes in the two groups are 276 and 138 subjects, respectively (a total sample size of 414 subjects).

Regarding the assessment of clinical superiority in DCNVA at 40 cm and DCIVA at 66 cm, the probability that the Test group’s mean logMAR VA will be at least 0.10 units less than the Control group’s mean logMAR VA will be 89% if the true difference is -0.12 units, 97% if the true difference is -0.13 units, and 99% if the true difference is -0.14 units, assuming that the common standard deviation is 0.15 when the sample sizes in the two groups are 276 and 138 subjects, respectively (a total sample size of 414 subjects).

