If there are missing mITT analysis set monocular DCNVA or DCIVA data at Visit 4, then missing data will be imputed using the Markov chain Monte Carlo multiple imputation method. After imputation of missing data, the statistical hypotheses will be tested using two-sided two-sample t-tests by imputation.

For each endpoint, an overall p-value resulting from the multiple imputation method will be estimated. The treatment effect (mean Test group IOL VA minus mean Control group IOL VA) in logMAR units will be summarized using continuous summary statistics and a two-sided 95% confidence interval. If the p-value from the multiple imputation analysis of treatment effect is less than or equal to 0.05 and the treatment effect is less than or equal to -0.10 logMAR units for DCIVA (i.e., the Test lens mean logMAR VA is at least 0.10 less than the mean for the control) or less than or equal to -0.20 logMAR units for DCNVA, then it will be concluded that the Test IOL is statistically and clinically successful in the corresponding outcome.

The previous continuous summary statistics will also be provided for the Per Protocol Set. However, superiority will not be evaluated with the PP Set, and statistical success will not depend upon the results of the PP analysis.

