Regarding the assessment of clinical superiority in DCNVA and DCIVA, the probability that the Test group's mean logMAR VA will be at least 0.1 units less than the Control group's mean logMAR VA will be 89% if the true difference is -0.12 units, 97% if the true difference is -0.13 units, and 99% if the true difference is -0.14 units, assuming that the common standard deviation is 0.15 when the sample sizes in the two groups are 276 and 138 subjects, respectively (a total sample size of 414 subjects).

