#### 13.5.3.2 Photopic Monocular DCNVA

Photopic monocular distance-corrected near visual acuity (DCNVA) at 40 cm in first eyes at Post-Operative Visit 4 will be summarized using continuous summary statistics in logMAR units by treatment assignment for the mITT Set Phase II and III subjects (combined). The DCNVA best distance data from the Phase I/Pilot subjects will be excluded from hypothesis testing and will be summarized separately from the data of the other subjects.

If there are missing mITT analysis set monocular DCNVA data at Visit 4, then missing data will be imputed using the Markov chain Monte Carlo (MCMC) multiple imputation method. After imputation of missing data, the statistical hypotheses will be tested using a statistical model with treatment and site as fixed factors by imputation.

An overall p-value resulting from the multiple imputation method will be estimated. The treatment effect (mean Test group IOL VA minus mean Control group IOL VA) in logMAR units will be summarized using continuous summary statistics and a two-sided 95% confidence interval. If the p-value from the multiple imputation analysis is less than or equal to 0.05 and the treatment effect is less than or equal to -0.20 (i.e., the Test lens mean logMAR VA is at least 0.20 less than the mean for the control), then it will be concluded that the Test IOL is statistically and clinically successful (i.e., superior to the Control IOL) in this outcome.

The previous continuous summary statistics will also be provided for the Per Protocol Set. However, superiority will not be evaluated with the PP Set and statistical success will not depend upon the results of the PP analysis.

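### The 89%, 97% and 99% clinical-superiority probabilities given for both DCNVA and DCIVA are computed at a 0.10 logMAR bar, but the protocol's clinical-success bar for DCNVA is 0.20, so they are valid for DCIVA only

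*Protocol*

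**What the plan says.** **Sample-size text.** Protocol 13.3.4 introduces its figures with "Regarding the assessment of clinical superiority in DCNVA at 40 cm and DCIVA at 66 cm". The event it evaluates is that the Test group's "mean logMAR VA will be at least 0.10 units less than the Control" group's mean. The probability of that event "will be 89% if the true difference is -0.12 units, 97% if the true difference is -0.13 units", and 99% at -0.14, for SD 0.15 and 276 and 138 subjects. The synopsis sample-size section repeats this ("will be 89% if the true difference is -0.12 units"), and so does SAP 6.4. No separate figures are given for DCNVA.

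**Success rule.** For monocular DCNVA, Protocol 13.5.3.2 requires p ≤ 0.05 and that "the treatment effect is less than or equal to -0.20 (i.e., the Test lens mean logMAR VA is at least 0.20 less" than the Control mean. The synopsis (Primary Effectiveness Analyses) sets the two bars in one sentence: -0.10 for DCIVA, "or less than or equal to -0.20 logMAR units for DCNVA". Protocol 13.5.3.3 confirms -0.10 for DCIVA.

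**SAP.** SAP 13.3.2 applies -0.10 to DCNVA. The table of changes in SAP section 16 does not list this as a departure from the protocol.

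**The concern.** The sample-size section and the analysis section of the same protocol describe different clinical criteria for DCNVA. The synopsis separates the two bars and 13.5.3.2 states 0.20 both as a number and in words, so the 0.20 does not look like a slip of the pen.

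A reader of 13.3.4 would conclude that a true near benefit of 0.12 to 0.14 logMAR makes it likely or nearly certain that the DCNVA clinical criterion is met. Under the protocol's own criterion, such a benefit makes a miss nearly certain. DCNVA is one of three primary effectiveness endpoints, and neither document gives the probability of meeting a 0.20 bar at any true effect.

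**Working it through.** **Inputs.** SD 0.15, n = 276 Test and 138 Control, and true differences -0.12, -0.13 and -0.14, all from Protocol 13.3.4. Bar 0.10 from 13.3.4 and 13.5.3.3 (DCIVA). Bar 0.20 from 13.5.3.2 and the synopsis (DCNVA).

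**Standard error of the difference in means.**

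SE = 0.15 × √(1/276 + 1/138) = 0.15 × √0.010870 = 0.01564

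**Probability that the observed difference meets the bar.**

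P = Φ((|true difference| − bar) / SE)

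| True difference | Stated | Bar 0.10 | Bar 0.20 |
|---|---|---|---|
| -0.12 | 89% | Φ(1.279) = 89.95% | Φ(-5.116) = 0.000016% |
| -0.13 | 97% | Φ(1.918) = 97.25% | Φ(-4.476) = 0.00038% |
| -0.14 | 99% | Φ(2.558) = 99.47% | Φ(-3.837) = 0.0062% |

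The plan's figures are reproduced at the 0.10 bar, which confirms how they were obtained.

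**What the 0.20 bar gives at larger true differences.**

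- -0.20: Φ(0) = 50%
- about -0.213: 80%
- -0.22: Φ(1.279) = 89.95%
- -0.23: Φ(1.918) = 97.25%
- -0.24: Φ(2.558) = 99.47%

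The whole scale moves by 0.10 logMAR.

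**Does the p-value condition matter?** No. The smallest significant observed difference is about 1.96 × 0.01564 = 0.031, so any difference that meets either bar is already significant.

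**Sensitivity to SD.** Protocol 13.3.5 uses SD 0.20 for binocular DCNVA. If that were assumed here, the 0.20 bar would give 0.006%, 0.04% and 0.20% at -0.12, -0.13 and -0.14. The conclusion does not change.

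**The case against.** **The arithmetic is right.** The sentence names its event as an advantage of at least 0.10, and for that event the percentages are correct. This stands. The defect is a mismatch between sections, not a miscalculation. But the sentence is presented as the clinical-superiority assessment for DCNVA, and the protocol makes that assessment at 0.20.

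**The figures agree with the SAP.** SAP 13.3.2 uses -0.10 for DCNVA, and SAP 6.4 matches it. This makes the correction conditional on which bar is final. It does not remove the contradiction inside the protocol, and the SAP does not declare the change.

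**Statistical success is defined without the bar.** Protocol 13.2.2 ties trial success to the statistical success of the three primary effectiveness endpoints. For DCNVA it defines this as rejecting the null with a lower Test mean. On that definition a true -0.12 lies 0.12/0.01564 = 7.7 standard errors from zero and succeeds almost surely. This stands: the small probabilities above concern the combined statistical and clinical criterion of 13.5.3.2, not the definition in 13.2.2.

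**A reader might infer that the trial is underpowered for DCNVA, or that it needs a true benefit of -0.22 to -0.24.** The documents support neither. They state no expected DCNVA effect, and the range -0.22 to -0.24 simply matches the stated probability levels; 80% would be reached at about -0.213. Protocol 13.3.7 attributes the 300 and 150 subjects to ANSI and ISO standards, not to these probabilities.

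**A reader might also fault the 99% power at -0.10.** The synopsis already labels that figure as belonging to the statistical superiority tests, with clinical superiority treated separately. It is not an error; 13.3.4 and SAP 6.4 are only less explicit.

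**Conclusion.** The point holds as an internal inconsistency in the protocol. The stated 89%, 97% and 99% are valid for DCIVA. For DCNVA they do not describe the protocol's clinical-success criterion: at the 0.20 bar the same true differences give at most about 0.006%, and comparable probabilities are reached only 0.10 logMAR further out. This assumes a normally distributed mean difference and the plan's own SD and evaluable numbers, without allowance for site adjustment or imputation, as in the plan's own calculation.

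The finding concerns a misstated justification. It is not evidence of a shortfall in power or sample size. If the DCNVA bar is finally set at -0.10, the present figures stand and it is the success rule in the protocol that has to change.

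**What to change.** 1. Reconcile the DCNVA clinical-success bar between the protocol (-0.20 in the synopsis and 13.5.3.2) and SAP 13.3.2 (-0.10). If the SAP is to differ from the protocol, list this in SAP section 16.
2. In Protocol 13.3.4, split the sentence by endpoint. Keep the present figures for DCIVA at its -0.10 bar.
3. For DCNVA, state the probabilities at the final bar. If it is -0.20: about 90%, 97% and 99% at true differences of -0.22, -0.23 and -0.24, and 50% at -0.20. If it is -0.10: the present figures stand, and the synopsis and 13.5.3.2 must be changed to match.
4. Carry the result to the synopsis sample-size section and SAP 6.4.
5. Optionally, label the 99% power in 13.3.4 and SAP 6.4 as the statistical test only, as the synopsis does.

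Steps 2 to 5 cost only wording, with no change to design or sample size. If -0.20 is kept, the stated DCNVA justification becomes less favourable. Step 1 needs a sponsor decision on the bar, best made and documented before unmasking.
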